4.5. Analysis of Safety Data

All safety analyses will be conducted in the Safety population. Subjects who receive the wrong study drug for their entire course of study drug will be analyzed in the treatment group based on the drug received. Subjects who receive the wrong study drug for part of their course of study

drug will be analyzed in the treatment group based on majority of (i.e., most frequent) doses received.

4.5.1. Adverse Events

Verbatim descriptions of AEs will be coded using the latest MedDRA version (version 23.0 or higher). Summary tables will be provided for all treatment-emergent adverse events (TEAEs). A TEAE is defined as an AE that occurs during or after study drug administration and up through the Follow Up visit (Days 52-59). An AE is programmatically defined as treatment emergent if the start date and time is on or after the start date and time of the first dose of study drug. If the time of an AE is missing, it is considered treatment emergent if it starts on the same date as the first dose of study drug. Date Imputations will follow the rules described in [Appendix 8 \(Section 5.8\)](#).

Deaths obtained only through the Survival Status eCRF will not be recorded on the AE eCRF, but will be programmed as an AE with SOC and PT of "Death NOS" and analyzed as an AE/SAE with outcome of fatal.

An overall summary of AEs and TEAEs will include the number and percentage of subjects in each treatment group who experienced at least 1 AE/TEAE in the following categories: any AE, any TEAE, any TEAE up through Day 7, any study drug-related TEAE, any grade 4/5 TEAE, any serious AE (SAE), any study drug-related SAE, any SAE leading to death (that includes SAE started during study with an outcome of death that occurred after the Follow-up Visit), any study drug-related SAE leading to death, any TEAE resulting in interruption of administration of study drug, any TEAE leading to discontinuation of study drug, and any TEAE resulting in study discontinuation. The overall summary of AEs will be repeated for the high risk subgroups defined in [Table 4-1](#).

Subjects with multiple events will be counted only once within each category. CTCAE grade (version 5.0) and relationship will be counted using the maximum grade and the strongest relationship respectively for a subject with multiple TEAEs.

The number and percentage of subjects reporting a TEAE in each treatment group will be tabulated by SOC and PT; by SOC, PT, and maximum CTCAE grade (1, 2, 3, 4, or 5); and by SOC, PT, and relationship (unrelated or related) to study drug. The incidence of TEAEs in each treatment group that occur up through Day 7 will be summarized by SOC and PT. The incidence of all TEAEs and all non-serious TEAEs that occur in at least 5% of subjects in the Rezafungin for Injection or caspofungin groups will be summarized separately by PT and treatment group, sorted by decreasing frequency in the Rezafungin for Injection group. The incidence of all TEAEs by SOC and PT will be also summarized by diagnosis (candidemia only versus IC) and by high risk subgroups defined in [Table 4-1](#). For all analyses of TEAEs, if the same TEAE (based on PT) is reported for the same subject more than once, the TEAE is counted only once for that PT and at the highest grade and strongest relationship to study drug.

The number and percentage of subjects in each treatment group reporting a SAE, reporting a study drug-related SAE, reporting a TEAE resulting in interruption of study drug administration,

reporting a TEAE leading to discontinuation of study drug, and reporting a fatal SAE will be summarized by SOC and PT. In addition to a listing of all reported AEs, by-subject listings of all SAEs (including any SAEs with an outcome of death), AEs of special interest, and all TEAEs resulting in the alteration of or leading to discontinuation of study drug will be provided.

The number and percentage of subjects in each treatment group reporting a potential Drug Induced Liver Injury Adverse Events (DILI, Hepatic transaminase and Bilirubin elevations) will be presented. The following combination of Standardized MedDRA query (SMQ)/PTs will be used: Cholestasis and jaundice of hepatic origin (SMQ, broad), Liver related investigations, signs and symptoms (SMQ, broad), Liver-related coagulation and bleeding disturbances (SMQ, broad), Hepatic failure, fibrosis and cirrhosis and other liver damage-related conditions (SMQ, broad), Hepatitis, non-infectious (SMQ, broad), Bilirubin conjugated (PT), Bilirubin urine (PT), Bilirubinuria (PT), Blood bilirubin (PT), Urobilinogen urine (PT), Urobilinogen faeces abnormal (PT), Urobilinogen faeces increased (PT), Urobilinogen faeces (PT).

Adverse Events of Special Interest (AESI)

All AEs will be reported, but certain adverse events of special interest will be specifically evaluated including but not limited to

- IV Infusion Intolerability Adverse Experiences
- Phototoxicity
- Ataxia, Neuropathy and Tremors (ataxia, axonal neuropathy, hypoesthesia, paresthesia, peripheral motor neuropathy, peripheral neuropathy, peripheral sensory neuropathies, peripheral sensorimotor neuropathy, polyneuropathy, toxic neuropathy, and tremors)

The number and percentage of subjects in each treatment group reporting AESI in the categories above will be reported. Additional analyses by higher risk subgroups might be considered. Higher risk subgroups that will be considered include but are not limited to:

Table 4-1: Higher Risk Subgroups

Elderly	≥65 years (yes/no)
Moderate hepatic impairment	Child-Pugh score of 7-9 (yes/no)
Higher weight	Baseline weight >80 kg (yes/no)
Neutropenia	(ANC<500, ANC≥500)
APACHE II score	(≥20, <20, 10-19, <10)
Diagnosis at Randomization	(candidemia only versus IC)

Subjects Diagnosed with COVID-19

Subjects diagnosed with COVID prior to entry into the study (based on medical history) or after the first dose of study drug (TEAE) will be presented in a listing with date of COVID-19 infection and outcome.

A table of TEAEs of coronavirus infection will be presented by PT and a listing of all TEAEs in subjects with diagnosed COVID-19 will be provided. Depending upon the number of subjects diagnosed with COVID-19, a summary of TEAEs by SOC and PT may be provided.

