12.2 Adverse Events

Adverse Events will be collected for all subjects from informed consent through Follow-up (Days 52–59). The Investigator will assess all AEs and SAEs and will record the following information on the appropriate eCRF page:

- Date of onset
- Date of resolution or stabilization
- Seriousness
- AE severity
- Causal relationship to study drug(s), including relationship to a specific study drug if a determination can be made
- Action taken with study medication

Medically indicated laboratory tests (emergency or unscheduled tests) should be conducted at the local laboratory. The Investigator should employ best medical judgment in determining how to manage AEs and SAEs. Any questions regarding AE or SAE management should be directed to the Medical Monitor.

The Sponsor is responsible for:

- Confirming the seriousness assessment of all reported AEs and SAEs
- Confirming the causal relationship between reported AEs/SAEs and the investigational product
- Assessment of SAEs for expectedness

The Sponsor will continuously assess the safety of the investigational product throughout the study.

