13.5 Safety Analyses

All safety analyses will be conducted in the Safety population and will be summarized by study drug actually received.

A TEAE is defined as an AE that occurs during or after the first dose of study drug up through the Follow-up visit (Days 52–59). An overall summary of AEs will be provided by treatment group. The incidence of TEAEs will be presented by SOC and Preferred Term (PT); SOC, PT

and relationship to the study drug administration; and SOC, PT, and CTCAE grade (version 5.0). Tables of any TEAE resulting in discontinuation of study drug and SAEs will also be provided. A table of TEAEs of coronavirus will be presented by PT and a listing of all TEAEs in subjects with COVID-19 (medical history or TEAE) will be provided. Depending upon the number of subjects diagnosed with COVID-19, a summary of TEAEs by SOC and PT may be provided.

Descriptive statistics for clinical laboratory test results (hematology and chemistry) will be presented for all study visits. The change from baseline to each post-baseline visit and to the overall worst post-baseline value will be summarized by treatment group. Laboratory values will be graded using CTCAE version 5.0 and shift tables will be provided. Liver enzymes will be classified as > ULN, >3×, >5× and >10×ULN and the number and percentage of subjects with any post-baseline value in one of the categories will be presented by study drug.

Descriptive statistics of vital sign parameters will be presented by treatment group and study visit, as well as the change from baseline at each study visit. Potentially clinically significant (PCS) values will be defined in the SAP and the number and percentage of subjects with a PCS value will be summarized by treatment group for the worst-post-baseline value.

Descriptive statistics of ECG parameters will be presented by treatment group and will include change from baseline.

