2.1.1. Estimand Framework

An addendum to ICH E9 introduces the concept of an estimand which translates the trial objective into a precise definition of the treatment effect that is to be estimated. The description of the estimand includes four attributes: the population, the variable (or endpoint) to be obtained for each patient, the specification of how to account for intercurrent events (ICE), and the population-level summary for the variable. These attributes are described below for the FDA and EMA primary efficacy outcomes.

Table 2-1: Estimand Attributes

	ACM at Day 30 (FDA)	Global Response at Day 14 (EMA)
Population	mITT Population (see Section 2.6)	mITT Population (see Section 2.6)
Variable/Endpoint	Deceased by Day 30	DRC global response of cure
Handling of intercurrent events	Treatment policy estimand as measured irrespective of any ICE 
 • Missing data considered deceased 	Composite estimand as the following ICE's are incorporated into the variable/endpoint: 
 • Death (failure) • Receipt of rescue therapy (failure) • Discontinuation of study drug due to an adverse event (failure) • Missing data (classified as indeterminate but analyzed as a failure)
Population-level summary	Difference between treatment groups in percentage of subjects who died	Difference between treatment groups in percentage of subjects with a DRC global response of cure

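### Interruption and discontinuation of study drug are tabulated for TEAEs only, so a non-serious AE with known pre-dose onset that stops or interrupts drug is in no by-arm SOC/PT safety table

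*SAP*

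**What the plan says.** Protocol 12.2 sets the collection period: "Adverse Events will be collected for all subjects from informed consent through Follow-up (Days 52–59"). AEs that start before the first dose are therefore recorded as AEs. The same section has the investigator record "Action taken with study medication" for each AE.

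Protocol 13.5 states: "A TEAE is defined as an AE that occurs during or after the first dose of study drug", with Follow-up as the end point. SAP 4.5.1 turns this into an onset rule, worded as follows: "programmatically defined as treatment emergent if the start date and time is on or after the start date and time of the first dose". Two provisions extend the rule. In SAP 4.5.1, an AE with a missing time that starts on the first-dose date counts as treatment emergent. In SAP Appendix 8, so does an AE that cannot be placed before or after the first dose.

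The overall summary in SAP 4.5.1 has rows for "any TEAE resulting in interruption of administration of study drug, any TEAE leading to discontinuation of study drug". The corresponding SOC/PT tables carry the same restriction. So does the dedicated listing, in which "all TEAEs resulting in the alteration of or leading to discontinuation of study drug will be provided".

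**The concern.** Action taken is an attribute of the AE record, whereas treatment emergence depends only on when that record starts. An event that begins after consent but before dosing can later be the reason for holding or stopping study drug, with no change in grade. Under the stated rule it never enters the outputs built to show which events interrupted or ended treatment.

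Safety and tolerability are a comparative objective set in the Safety population (SAP 1.1.2). Interruption and discontinuation by SOC/PT and arm are among the main tables for that comparison. For the events described here, a reader could learn that a subject stopped drug but could not see the event in any by-arm table.

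**Working it through.** The documents give no figure to reproduce, so the check applies the stated selection rules to a test record.

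**Test record.** Non-serious AE; onset after consent and on a known date before the day of first dose; one record; grade unchanged; action taken is study drug interrupted or withdrawn.

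| Output | Selected on | Test record shown? |
|---|---|---|
| Overall summary, all-AE row (SAP 4.5.1) | Any AE | Yes, as a count without the event |
| Overall summary, TEAE rows, including interruption and discontinuation (SAP 4.5.1) | TEAE | No |
| SOC/PT tables, including by grade and by relationship (SAP 4.5.1) | TEAE | No |
| Interruption and discontinuation tables by SOC/PT (SAP 4.5.1) | TEAE | No |
| SAE and fatal SAE tables (SAP 4.5.1) | Serious events | No, because it is non-serious |
| Special-interest and liver-injury counts (SAP 4.5.1) | Not stated to be TEAE-only | Only if the event falls in those categories |
| Listing of events altering or stopping drug (SAP 4.5.1) | TEAE | No |
| Listing of all AEs (SAP 4.5.1); listings of all eCRF data (SAP 3.2) | Any AE | Yes, by subject |
| Disposition (SAP 4.1.1) | Reason for stopping treatment; ITT and mITT | Reason only, and only if drug is stopped |

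The record is in no by-arm SOC/PT table in the Safety population. An interruption without discontinuation does not reach disposition either.

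**How many records could be affected.** The documents give no count, and several provisions keep the set small:
- Screening lasts at most 96 hours (Protocol 6.4), AEs count only from consent, and randomization comes just before dosing (Protocol 9.2.1).
- Onset on the first-dose date with no time recorded is already treatment emergent. Protocol 12.2 lists a date of onset and no time.
- Onset that cannot be ordered relative to the first dose is already treatment emergent (SAP Appendix 8).
- Non-serious events related to the candidemia or invasive candidiasis itself are not recorded as AEs (Protocol 12.4.1).

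**Size per subject.** Input: 218 randomized 1:1 (Protocol 13.8). Assumption: all are treated.
- Subjects per arm: 218 / 2 = 109.
- One omitted subject: 1 / 109 = 0.92 percentage points, and only if that subject has no other event qualifying for the same row.
- Assumed range of 0 to 3 subjects per arm: 0 to 3 / 109 = 0 to 2.75 points. This range is illustrative and has no source in the documents.

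**The case against.** The strongest reply is that nothing is lost and the restriction is a legitimate choice. The event and the action taken can be found in the by-subject listings. An AE that predates the drug and does not worsen is not treatment emergent under any usual definition, and Protocol 13.5 itself specifies the discontinuation table for TEAEs. The disposition tables also cover all randomized subjects, so their difference from the Safety population is slight: untreated subjects and wrong-drug assignments. All of this stands, and it is why the point is minor. What it leaves open is that a by-subject listing is not a comparison by arm, and a disposition category does not name the event.

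Three stronger readings are tempting, and the documents support none of them.

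- *A reader might infer that on-treatment worsening of pre-dose AEs is generally lost from the TEAE and grade tables.* That depends on whether sites open a new record when the grade rises, which neither document says. If they do, the new record has a post-dose start and is already a TEAE.
- *A reader might infer that the safety table contradicts the efficacy rule*, because SAP Table 2-1 counts as failure "Discontinuation of study drug due to an adverse event (failure"), with no TEAE limit. That is a composite rule for the mITT population at a visit; the safety table describes TEAEs in the Safety population through Follow-up. Nothing requires the two to agree.
- *A reader might infer that serious events drop out too*, because the SAP abbreviation list expands SAE as a treatment-emergent term. The operative text in SAP 4.5.1 refers to any serious AE, so the abbreviation is a clerical slip.

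**Conclusion.** The point holds in a narrow form. A non-serious AE with known pre-dose onset, kept as one record, that leads to interruption or discontinuation of study drug is missing from every by-arm SOC/PT table in the Safety population. This follows directly from the stated selection rule and needs no assumption about worsening.

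Severity is minor. The number of such events is unknown and probably very small. Each affected subject is worth about 0.9 points of an arm, assuming 109 treated per arm. The events remain in the listings, and the primary efficacy analyses do not use the TEAE flag.

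**What to change.** In the SAP, select the interruption and discontinuation rows, their SOC/PT tables and the dedicated listing on any AE, using the action-taken item already collected under Protocol 12.2, and show TEAEs as a subset. Keeping the subset still delivers the table that Protocol 13.5 specifies, so no protocol amendment is needed. SAP 1.1.1 provides for a SAP amendment before database lock, or a description in the study report afterwards. The cost is a changed selection rule and slightly higher counts in both arms.

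Optionally, add to the SAP definition of a TEAE an AE that starts before the first dose and worsens on or after it. With the fields listed in Protocol 12.2 this gains little. Only a fatal outcome carries a date for the worsening, so only fatal events would newly enter the TEAE and grade 4/5 outputs, and these are already in the SAE tables. Non-fatal worsening on a single record cannot be dated.

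As a clerical correction, expand SAE in the SAP abbreviation list as serious adverse event.

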4.5.2. Clinical Laboratory Data

Several analyses of clinical laboratory data will be presented. For descriptive statistics of actual values and the change from baseline, values will be normalized against normal ranges from a common source (US National Library of Medicine [NLM], MedlinePlus) according to the following Scale Model formula (Karvanen, 2003): $s = x (U_s/U_x)$, where s = the individual laboratory value normalized against the laboratory normal range from the common source; x = the original individual laboratory value; U_x is the upper limit of the normal range for an individual laboratory parameter; U_s is the upper limit of the laboratory normal range for that laboratory parameter from the common source. WBC differentials in percent that are derived from the absolute counts will not be normalized because of the missing upper limit of the normal range in percent. For WBC differentials in percent with the non-missing upper limit, the maximum of the normalized values will be limited to 100%. Coagulation lab tests and urinalysis tests will not be normalized.

Descriptive statistics (based on Systeme Internationale [SI] units) for chemistry and hematology parameters, as well as the change from baseline, will be summarized by treatment group for all study visits and for the worst overall post-baseline value. The directionality for determining the worst overall post-baseline value is provided in [Section 5.5](#). Change from baseline will be calculated for each subject at the specified time point as the value at the specified time point minus the baseline value. If multiple values are obtained during the Screening period, the last non-missing values collected prior to the first dose of study drug will be used for the baseline.

The laboratory values will be graded using the CTCAE version 5.0. If no CTCAE grade is available, Division of Microbiology and Infectious Disease (DMID) or Division of AIDS (DAIDS) will be used for grading. Shift tables will be presented to show the number of subjects with each toxicity grade (1,2,3, or 4/5) at baseline versus each post-baseline visit and the worst post-baseline grade (including any unscheduled visits). For those laboratory parameters for which high toxicity grades are specified for both low and high values (e.g., sodium, potassium), shifts in toxicity will be presented for high and low toxicities separately. The percentages will be based on the number of subjects with both a baseline and post-baseline (at the specified visit) assessment of the specific laboratory parameter. The number and percentage of subjects with at least a 2-grade increase from baseline at any post-baseline study visit, including unscheduled visits, will be summarized by laboratory parameter and treatment group. Percentages for each lab test will be based on the number of subjects with both a baseline and a post-baseline evaluation of the particular laboratory test. A listing will be provided which provides all results for a given laboratory test for subjects who have at least one 2-grade increase from baseline.

Detailed subject listings of all laboratory data (including coagulation and urinalysis results) collected during the study will be provided. Laboratory values outside normal limits will be identified in the subject data listings. A column will display any applicable toxicity grading of the laboratory value. The results from pregnancy tests will also be listed.

Hepatic Safety Data

Hepatic effects (liver function test (LFT) abnormality) will be identified with selected adverse events (as defined in [Section 4.5.1](#) [Adverse Events of Special Interest]), and the laboratory parameters: AST (aspartate aminotransferase), ALT (alanine aminotransferase), ALP (alkaline phosphatase) and TBL (total bilirubin).

Threshold values of interest for liver function tests are given below in **Table 4-2**: Criterion-based hepatic events

. The laboratory results meeting specified criteria standard table will be used to provide the number and percentage of patients having AST, ALT > 3, 5, 8, 10 x upper limit of normal (ULN) or TBL >1.5, 2 x ULN or ALP > 2, 3 x ULN and any other criteria specified in **Table 4-2**:
Criterion-based hepatic events

at any time post-baseline regardless of their baseline value. For a combined criterion to be fulfilled, all conditions must be fulfilled on the same lab measurement.

The number and percentage of potential Hy's Law cases will be presented by treatment group. The criteria for Hy's law is: (ALT or AST) >3 ×ULN, ALP ≤2.0 ×ULN, and total bilirubin >2 ×ULN. A listing of subjects who meet either laboratory criteria for Hy's law will also be provided. Subjects meeting either criteria based on any combination of post-baseline laboratory results, irrespective of their temporal association, as well as subjects meeting the criteria at the same time point, will be listed. All laboratory results for the parameters included in the criteria will be presented by visit for all subjects who meet the criteria.

Table 4-2: Criterion-based hepatic events

Parameter	Criterion
ALT	>3xULN; >5xULN; >8xULN; >10xULN
AST	>3xULN; >5xULN; >8xULN; >10xULN
ALT or AST	>3xULN; >5xULN; >8xULN; >10xULN
TBL	>1.5xULN; >2xULN
ALP	>2xULN; >3xULN
(ALT or AST) & TBL	ALT or AST >3xULN & TBL >2xULN ALT or AST >5xULN & TBL >2xULN ALT or AST >8x ULN &TBL >2xULN ALT or AST >10xULN & TBL >2xULN
(ALT or AST) & TBL & ALP	ALT or AST >3xULN & TBL > 2.0xULN & ALP ≤2xULN (potential Hy's Law)

AST = Aspartate aminotransferase; also known as SGOT, ALT = Alanine aminotransferase; also known as SGPT, ALP = Alkaline phosphatase, TBL = Total bilirubin.

Nephrotoxicity

To evaluate the effect of Rezafungin for Injection on renal function, nephrotoxicity is defined as doubling of serum creatinine relative to baseline or an increase of ≥ 1 mg/dL in serum creatinine if baseline serum creatinine was above the upper limit of the normal range. The observed proportions of subjects with nephrotoxicity by visit and worst post-baseline value will be reported by treatment group.

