Use of concomitant cyclosporine should be limited to subjects for whom potential benefit outweighs potential risk of DDIs and hepatotoxicity with caspofungin.

Oral Step-Down Regimen: Fluconazole

After ≥ 3 days of caspofungin treatment (or the minimum duration of IV therapy advised by the site's national/regional/local guidelines, whichever is greater), subjects who meet the step-down therapy eligibility criteria may be switched to oral fluconazole (earliest oral dose on Day 4 or later, as advised by a site's national/regional/local guidelines). The total comparator treatment period (caspofungin plus fluconazole) is ≤ 28 days. Subjects weighing over 130 kg will not be eligible for oral step-down therapy. Subjects with a creatinine clearance > 50 mL/min (see [Appendix 2](#)) will receive oral fluconazole at a dose of 6 mg/kg administered once daily rounded to the nearest 200 mg increment with a maximum daily dose of 800 mg (e.g., a subject weighing 73 kg would receive a fluconazole 400 mg dose [2 capsules of 200 mg each] based on a 6 mg/kg target dose [$73 \text{ kg} \times 6 \text{ mg/kg} = 438 \text{ mg}$]). Subjects with creatinine clearance ≤ 50 mL/min will receive oral fluconazole at a dose of 3 mg/kg administered once daily rounded to the nearest 200 mg increment with a maximum daily dose of 400 mg (e.g., a subject weighing 73 kg would receive a fluconazole 200 mg dose [1 capsule of 200 mg] based on a 3 mg/kg target dose [$73 \text{ kg} \times 3 \text{ mg/kg} = 219 \text{ mg}$]). Subjects receiving hemodialysis receive the same dose as subjects with a creatinine clearance > 50 mL/min; however, they are only dosed following hemodialysis. Subjects receiving continuous renal replacement therapy (CRRT) should be treated as a subject with normal renal function at 6 mg/kg rounded to the nearest 200 mg each day ([Cousin 2003](#)). Subjects receiving peritoneal dialysis should be treated with 1.5 mg/kg rounded to the nearest 200 mg each day ([Cousin 2003](#)). Investigators are advised to pay close attention to signs of overdosing and underdosing with underweight (< 50 kg) and overweight (> 85 kg) subjects, respectively. Additionally, signs of potential fluconazole toxicity, including hepatic toxicity and QT prolongation, should be closely monitored for any subject on oral step-down therapy.

Oral Step-Down Therapy Eligibility Criteria

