The number and percentage of subjects with each of the following risk factors at Screening will be summarized by treatment group in the ITT and mITT populations.

Risk factors for candidemia and IC include (but are not limited to):

- Central venous catheter
- PICC (Peripherally Inserted Central Catheter)
- Active malignancy
- Broad-spectrum antibiotic therapy
- Diabetes mellitus
- Immunosuppression
- Major surgery
- Total parenteral nutrition
- Transplant recipient
- Trauma
- End stage renal disease/ dialysis
- Burns

- Pancreatitis
- Other

For subjects who had a catheter and positive blood culture at Screening, a summary of the number and percentage of subjects by type of catheter will be provided. Descriptive statistics for the durations of catheter placement (any catheter and by type of catheter) since the catheter placement and since diagnosis (the first positive blood culture) will also be provided. The durations are defined as the number of days since the catheter placement or the number of hours since the first positive blood culture (if catheter was already in place prior to the first positive blood culture) to the catheter removal date and time. The catheters that were removed prior to the first positive blood culture are not included in the summary. If there is more than one catheter placed across multiple locations, the one with the longest duration is summarized. The number and percent of subjects who had their catheter removed within 48 hours after diagnosis with candidemia and subjects who did not have their catheter withdrawn will be summarized by treatment group in the mITT population. This analysis will be repeated for the subjects diagnosed with candidemia only in the mITT population.

4.1.6. **Systemic Signs of Candidemia and/or IC**

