- Systemic antifungal medications received prior to the first dose of study drug (mITT population)
- Systemic antifungal medications (excluding study drug) received on/after the first dose of study drug through the Follow-up visit (mITT population)
- Non-antifungal medications received prior to the first dose of study drug (Safety population)
- Non-antifungal medications received on/after the first dose of study drug through the Follow-up visit (Safety population).

By-subject listings for non-antifungal medications and antifungal medications received prior to the first dose or administered after the first dose of study drug through the FU visit will be provided separately for the Safety population.

4.2.3. **Concomitant Procedures**

Concomitant procedures will be summarized by treatment group, SOC, and PT using the latest version of MedDRA in the mITT population. If the same procedure (based on PT) is reported for the same subject more than once, the procedure is counted only once for that PT. Procedures are considered concomitant if they are performed on or after the first dose of study drug (start date and time [if applicable] is on or after the first dose of study drug, stop date and time [if applicable] is after the first dose of study drug), or if the stop date is unknown or continuing.

A by-subject listing will display procedures on/after the first dose of study drug through the FU visit and will include the verbatim description of the procedure, MedDRA PT, reason for the procedure, and date and time of the procedure.

By-subject listings for transfusions and hemodialysis received prior to the first dose or after the first dose of study drug through the FU visit will be provided separately for the Safety population.

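### The nephrotoxicity rule in SAP 4.5.2 uses serum creatinine alone, so renal replacement therapy can produce, prevent or mask a flag in that one descriptive safety proportion

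*SAP*

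**What the plan says.** SAP 4.5.2 introduces the rule with the purpose "To evaluate the effect of Rezafungin for Injection on renal function". In full, "nephrotoxicity is defined as doubling of serum creatinine relative to baseline", or as a rise of at least 1 mg/dL, the second limb applying only "if baseline serum creatinine was above the upper limit of the normal range". The output is then specified: "The observed proportions of subjects with nephrotoxicity by visit and worst post-baseline value will be reported by treatment group". Under SAP 4.5 the population is the Safety population.

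The other elements that determine a flag are:

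- Baseline is the latest available value before first dose (SAP 4.5.2), with no rule on timing against dialysis.
- The worst creatinine is the highest one (SAP 5.5, Table 5-1). Unscheduled and out-of-window values enter the worst-value summary but not the by-visit summaries (SAP 3.8).
- Chemistry is scheduled at Screening, Days 1, 2, 4, 8, 14 and 30, end of treatment and Follow-up (Protocol 6.1.8).

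Subjects on renal replacement are foreseen. No exclusion criterion in Protocol 7.2 names renal failure or dialysis. The fluconazole rules in the Synopsis and in Protocol 8.2.3.5 cover hemodialysis ("they are only dosed following hemodialysis"), CRRT and peritoneal dialysis. SAP 4.1.5 tabulates "End stage renal disease/ dialysis" as a baseline risk factor by arm. SAP 4.2.3 summarises coded concomitant procedures by arm in the mITT population and adds, for the Safety population, "By-subject listings for transfusions and hemodialysis received prior to the first dose or after the first dose of study drug through the FU visit". None of these records is linked to the nephrotoxicity definition.

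**The concern.** A creatinine-change rule assumes that a change in the measurement reflects a change in the kidney. Under renal replacement that assumption can fail in two ways.

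- **False flag, or its absence.** On intermittent dialysis, creatinine falls with a session and climbs until the next. Baseline in such a subject will typically exceed ULN, so a rise of 1 mg/dL is enough. Taking the highest of many later values favours a between-session peak. The protocol recognises session timing for pharmacokinetic samples (Protocol 6.1.9) but not for chemistry.
- **Missed event.** Once renal replacement starts in a subject with new renal failure, it lowers creatinine. If no recorded value has crossed the threshold by then, the subject is not counted, and starting renal replacement is not itself an event.

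At stake is the accuracy of the proportion that the SAP presents as its measure of drug effect on renal function.

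**Working it through.** The plan states no expected rate, power or sample size for nephrotoxicity, so there is no figure of its own to reproduce. The check applies the rule literally to hypothetical series and then sizes the false flags under stated assumptions.

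**Rule.** Flag if value ≥ 2 × baseline, or if baseline > ULN and value − baseline ≥ 1 mg/dL. For illustration ULN is the male reference in SAP 5.7: 114.92 µmol/L ÷ 88.4 = 1.30 mg/dL.

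| Hypothetical subject (mg/dL) | Baseline | Lowest value that flags | Later values | Result |
|---|---|---|---|---|
| (a) Chronic hemodialysis, baseline after a session | 4.0 | 4.0 + 1 = 5.0 | 5.2, 4.1, 6.0, 4.0 | Flagged at 5.2, 6.0 and worst value |
| (b) Chronic hemodialysis, baseline before a session | 6.0 | 6.0 + 1 = 7.0 | 4.0, 5.8, 6.2 | Never flagged |
| (c) New renal failure, CRRT started after 2.2 | 1.2 | 2 × 1.2 = 2.4 | 1.4, 2.2, 1.6, 1.3 | Never flagged |
| (d) New renal failure, CRRT started after 2.9 | 2.0 | 2.0 + 1 = 3.0 | 2.3, 2.9, 1.8, 1.5 | Never flagged |
| (e) New renal failure, dialysis started after 2.6 | 1.2 | 2 × 1.2 = 2.4 | 1.4, 2.6, 1.6 | Flagged |

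Subjects (a) and (b) have no change in kidney function and differ mainly in when the baseline sample was drawn. Subjects (c) and (d) are real renal events that go uncounted; (e) shows that a miss is not certain.

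The creatinine grade tables in SAP 4.5.2 only partly compensate. Subject (a) stays at grade 3 throughout. Subject (c) moves from grade 0 to grade 2 (2.2 ÷ 1.30 = 1.69 × ULN) and so enters the 2-grade-increase summary. Subject (d) is grade 2 at baseline (2.0 ÷ 1.30 = 1.54) and at peak (2.9 ÷ 1.30 = 2.23) and does not.

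**Size of false flags.** Let n be subjects per arm, p the share on dialysis at baseline, f the share of those flagged by timing, and t the rate in everyone else. Taking n = 218 ÷ 2 = 109 treats all randomized subjects as dosed. The values of p, f and t are assumptions; the documents give none of them.

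- False flags per arm = n × p × f. Low: 109 × 0.05 × 0.30 = 1.6. High: 109 × 0.15 × 0.60 = 9.8. That is 1.5 to 9.0 percentage points.
- Reported rate = p × f + (1 − p) × t. With t = 5%: low 0.015 + 0.95 × 0.05 = 6.3%; high 0.09 + 0.85 × 0.05 = 13.3%.

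**Effect on the comparison.** If p and f are equal in both arms, the p × f terms cancel and the observed difference is (1 − p) times the true one. A 5-point difference becomes 0.95 × 5 = 4.75 to 0.85 × 5 = 4.25 points.

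**The case against.** The strongest reply is that this is one supplementary laboratory proportion and that the rest of the safety reporting covers the gap. Much of that stands.

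- A reader might infer that new dialysis vanishes from the safety evaluation, or that dialysis is visible only in a listing. The documents do not support either. Protocol 12.4.1 has a laboratory abnormality that belongs to a clinical condition recorded as the diagnosis, and renal failure needing dialysis could meet the seriousness criteria in Protocol 12.4.4. SAP 4.5.1 tabulates TEAEs and SAEs by arm. Dialysis also appears by arm among the risk factors (SAP 4.1.5) and, where coded as a procedure, in SAP 4.2.3.
- A reader might infer that dialysis swings always count and new dialysis is always missed. Subjects (b) and (e) show otherwise. Early scheduled chemistry and the inclusion of unscheduled values make a crossing before renal replacement more likely to be recorded.
- The session mechanism belongs to intermittent dialysis; CRRT is continuous, so it should not be carried over to every modality.
- A reader might infer bias between arms. Randomization balances dialysis on average, and with balance the dilution is small. Dialysis is not a stratification factor (SAP 1.2.1), so chance imbalance remains possible.

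What does not stand is that these other outputs repair the proportion. None of them feeds it. The procedure table is in the mITT rather than the Safety population, and the dedicated listing names hemodialysis only.

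**Conclusion.** The point holds as a misclassification problem. The rule as written can flag a subject on intermittent dialysis because of sample timing, and can omit a subject who starts renal replacement before any recorded creatinine reaches the threshold. Both are conditional on timing rather than certain.

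The consequence is noise, some inflation of each arm's rate and slight dilution of the difference, in one descriptive safety proportion. Primary endpoints, alpha and power are untouched. The figure of about 1.6–9.8 false flags per arm rests entirely on the assumed 5–15% dialysis prevalence and 30–60% flagging rate and is an illustration, not an estimate. The number of missed events cannot be sized from the documents. The change is worth making because a stated rule gives wrong classifications and the correction is cheap, not because a trial conclusion depends on it.

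**What to change.** Amend the nephrotoxicity paragraph of SAP 4.5.2:

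1. Exclude subjects on any renal replacement at baseline from numerator and denominator, and report them separately by arm. Identify them from medical history and from dated procedure and hemodialysis records. The SAP 4.1.5 category will not serve alone: it merges end stage renal disease with dialysis, and risk factors cover the previous 3 months (Protocol 9.1).
2. In subjects not on renal replacement at baseline, count the first post-dose start of hemodialysis, CRRT or peritoneal dialysis as a nephrotoxicity event.
3. Do not apply the doubling or 1 mg/dL criteria to creatinine values obtained after that start.

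The definition as it now stands can be kept as a sensitivity summary.

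The cost is a paragraph of SAP text, a slightly smaller denominator and some programming to find CRRT and peritoneal dialysis among coded procedures. The change relies largely on records already collected. SAP 1.1.1 provides for an amendment before database lock and for description in the study report afterwards; SAP 1.2.2 also plans an addendum for the second lock.
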